#### **4.6.1 Stopping Criteria for Individual Subjects**

The infusion for any individual subject will be stopped if the subject experiences a SAE or a clinically significant possibly drug-related related AE during the infusion, which in the opinion of the study physician, Principal Investigator, or Sponsor's medical representative, warrants discontinuation of the infusion for that subject's well-being.

#### **4.6.2 Criteria for Stopping Dose Escalation**

The decision to stop dose escalation will be at the discretion of the DRC and all the criteria leading to this decision will be documented in the meeting minutes.

If the DRC decides not to dose escalate, the current cohort may be expanded, if not already at the maximum size, following which further dose escalation could proceed. If the decision is to de-escalate to the prior cohort, up to 8 subjects randomized (6:2, JK07:placebo), without an additional unblinded sentinel subject may be added to the cohort, after which, safety and tolerability will be reassessed. If the decision is to de-escalate to an intermediate dose between the prior cohort and the cohort at which dose escalation was halted, the cohort will comprise a single sentinel subject receiving JK07 followed by randomization of a minimum of 4 subjects (3:1, JK07:placebo) in the cohort. See [Section 9.6](#) for details regarding the number of subjects to be enrolled in de-escalated or intermediate de-escalated cohorts.

#### **4.6.3 Criteria for Stopping the Study**

Criteria for stopping the study will be at the discretion of the DRC and all decisions taken will be clearly documented in the meeting minutes. This decision will be based on the cumulative evaluation of the study results and include not only DLAE but also safety concerns other than DLAEs which may arise.

## 5.0 STUDY POPULATION

Prospective approval of protocol deviations to recruitment and enrollment criteria, also known as protocol waivers or exemptions, is not permitted.

### 5.1 Inclusion Criteria

Subjects are eligible to be included in the study only if all of the following criteria apply:

1. 18 to 80 years of age, with stable NYHA Class II or III HF diagnosis, evident at least 6 months prior to enrollment as confirmed by medical history.
2. Stable HF defined as no hospitalizations for cardiac-related issues within the previous 2 months prior to the screening visit or between screening and randomization, other than for routine percutaneous procedures such as device, battery, generator changes or pacemaker lead insertion/replacement.
3. Subjects with clearly interpretable ECHO images and with a screening LVEF  $\leq 40\%$  in the absence of  $\geq$ Grade 3 valvular disease on 2D-TTE.
4. Subjects must be taking clinician-directed appropriate pharmacological therapy for HF as per the 2017 ACC/AHA/HFSA treatment guidelines (Yancy et al, 2017) and at investigator determined discretion at stable doses (except for diuretics) for at least 2 months prior to informed consent.
5. Subjects without implantable cardioverter-defibrillators (ICDs) are eligible. Subjects with ICDs are allowed at the discretion of the investigator, but only if both of the following criteria are met:  
(a) paced beats cannot exceed 15% of beats as quantified by screening e-Patch, and (b) if a non-paced baseline ECG can be obtained on Day 1 prior to study drug administration.
6. Body mass index  $\geq 18 \text{ kg/m}^2$  and  $\leq 45 \text{ kg/m}^2$
7. Screening hemoglobin  $\geq 9.0 \text{ g/dL}$ , platelets  $\geq 100 \times 10^9 / \text{mL}$ , ANC  $\geq 1500 / \text{mL}$ .
8. Sexually mature male subjects must agree to use a medically accepted method of contraception throughout the study and be willing and able to continue contraception until the end of the study (6-month time point).
9. Females of childbearing potential must present with a negative blood pregnancy test, must not be lactating, and must agree to employ adequate birth control measures for the duration of the study and be willing and able to continue contraception until the end of the study (6-month time point).
10. Subject is capable of giving signed informed consent as described in [Section 11.0](#) Appendix 2, which includes compliance with the requirements and restrictions listed in the informed consent form (ICF) and in this protocol.
11. Subject is willing and able to comply with the requirements of the protocol.

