#### 4.6 Study Stopping Criteria

Intravenous administration for any individual subject will be stopped if the subject experiences a serious adverse event (SAE) or a clinically significant, drug-related AE during the infusion, which in the opinion of the study physician, Principal Investigator, or Sponsor's medical representative, warrants discontinuation of the study for that subject's well-being. The definitions of an AE and an SAE can be found in [Section 8.3](#).

The final determination of whether any AE observed following JK07 administration is considered dose-limiting will be at the discretion of the DRC. Guidance provided to the DRC will be to view as a possible DLAE any AE at least possibly related to IP that results in any new finding of the following if observed within the first 15 days of treatment (DLAE assessment period):

- Any febrile neutropenia [absolute neutrophil count (ANC)]  $<1000/\text{mm}^3$ , temperature  $>38.3\text{ }^{\circ}\text{C}$  ( $101\text{ }^{\circ}\text{F}$ ) for  $>1$  hour.
- Any signs and/or symptoms of myocardial ischemia/myocardial infarction (diagnosis to be based on Thygesen et al. 2018), and any asymptomatic/symptomatic significant ( $> 2$  mm for  $> 2$  minutes) new ST segment deviation (elevation or depression), as defined in Hicks et al. 2018.
- Any emergent symptomatic or asymptomatic cardiac arrhythmia requiring at least urgent medical intervention.
- Any  $\geq$  QTc(F) prolongation of  $>500$  msec or  $>60$  msec above baseline (based on an average QTcF value of triplicate ECGs).
- Any emergent  $\geq$  severe (corresponding to CTCAE v5 Grade 3) hematologic, non-hematologic, hepato-cellular, or renal toxicity except for untreated nausea, diarrhea, vomiting, constipation, abdominal pain. Any of these will be considered DLTs if persisting  $>72$  hours despite appropriate treatment.
- Any at least moderate CD4 lymphocyte count  $\leq 400\text{ mm}^3$ .
- Any at least moderate infusion-related reaction or inability to deliver a complete dose due to possible treatment-related toxicity.
- An AE or SAE that, in the opinion of the DRC, is of potential clinical significance such that further dose escalation would expose subjects to unacceptable risk. In addition, the DRC may identify as a DLAE, any AE that impairs daily function, or abnormality occurring in subjects treated with JK07 at any time during the trial.

Each DLAE must be recorded in the eCRF.

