### **8.2.5      Electrocardiograms**

During Screening and beginning no more than 45 days before Day 1, all subjects will be supplied with, and instructed how to use a e-Patch for continuous 14-day heart rhythm monitoring as outlined in the Table 1 SoA. A 14-continuous day heart rhythm monitoring assessment will be collected using the e-Patch with monitoring completed no later than Day -10 unless confirmed with the sponsor.

Triplicate 12-lead ECGs will be performed prior to PK sample collection as outlined in [Table 1](#) and [Table 2](#). Local site will calculate heart rate and measure HR, PR, QRS, QT, and QTcF intervals for the first 48 hours. Where applicable, the screening ECG and Day 1 baseline ECG must be obtained without evidence of pacing.

All required ECG leads will be secured to the patient and attached to an ECG machine prior to administration of the IP to facilitate immediate post-infusion recording.

Subject should be supine for  $\geq 5$  minutes prior to each ECG performed.

At each time point at which triplicate ECGs are required, 3 individual ECG tracings should be performed as closely as possible in succession but no more than 2 minutes apart. The full set of triplicates should be completed in  $< 5$  minutes with no more than 2 min between them.

All ECGs must be collected prior to simultaneously scheduled blood sample collections (PK, biomarker, and/or laboratory assessments).

In the first 48-hours hours post-infusion, ECGs and PK samples must be performed in close proximity (within 10 minutes up to 4 hours postdose and after the 24- and 48-hour ECGs clock-time matched to the baseline ECG; within 30 minutes prior at other times greater than 4 hours postdose).

For safety reasons triplicate 12-lead ECGs will be printed and evaluated onsite.

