#### **G. Electrocardiograms (Digital 12-Lead Triplicate ECGs)**

Each subject will receive triplicate, twelve-lead ECG evaluations including HR, PR, QRS, QT (uncorrected), QTcF (corrected), and an overall evaluation of normality and clinical significance during screening and starting on Day 1 following admission to the hospital. ECG data will be collected, reviewed and analyzed by a Central Reader and the Principal Investigator. Findings identified by the Central Reader will be listed only for the concerned subjects.

The triplicate measurements of each subject at each timepoint will be averaged before summary. The observed values and mean CFBL of these ECG measurements will be summarized by cohort at each timepoint using descriptive statistics including 90% confidence interval of the mean. The overall ECG evaluation results, alone with shift from baseline (from abnormal to normal, or from normal to abnormal) will be summarized in a separate table by each treatment cohort and aggregated placebo at each visit. Results collected by the Central Reader and the Principal Investigator will be displayed separately.

Categories of QT and QTcF intervals (431-450 ms and >450 ms for males, and 451-470 and >470 ms for females) and CFBL in QT and QTcF intervals (30-60 ms, and >60 ms) will be summarized using counts and percentages by cohort and sampling time. Additional corrections to QT may be analyzed in a similar way. Results collected by the Central Reader and the Principal Investigator will be displayed separately.

A significant proportion of HFrEF patients with pre-existing implanted functional atrio-ventricular (A-V sequential) pacemakers and cardiac resynchronization devices (CRT), may be unevaluable with respect to QT/QTc analysis due to the inherently prolonged and fixed QRS configuration. The presence of these devices, which include defibrillators, is not considered an increased safety risk.

The electrocardiogram analysis will be conducted by cohort in the following two groups and presented separately:

- All subjects
- Subjects not having pacemakers identified by the contents of ECG overall evaluation. If none of the ECG evaluations have the word “pace” or “paced” or “pacemaker” or “electronic” or “electronically” or “resynchronization” or “CRT” for a subject, the subject is considered not to have a pacemaker or CRT (cardiac resynchronization therapy).

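### The paced-beat limit in inclusion criterion 5 covers only ICD carriers, so an intermittently paced pacemaker or CRT-P subject can have an unpaced baseline and paced post-dose QTcF

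*Protocol*

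**What the plan says.** Criterion 5 splits candidates by whether they have a defibrillator: "Subjects without implantable cardioverter-defibrillators (ICDs) are eligible. Subjects with ICDs are allowed at the discretion of the investigator". The first group faces no condition. The second group must meet two. One is a cap on pacing: "paced beats cannot exceed 15% of beats as quantified by screening e-Patch". The other is that a Day 1 ECG free of pacing is available before dosing. The protocol's abbreviation list defines ICD as an implantable cardioverter-defibrillator, so the term does not cover a plain pacemaker or a CRT-pacemaker.

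Section 8.2.5 adds a requirement that is not tied to ICDs: "Where applicable, the screening ECG and Day 1 baseline ECG must be obtained without evidence of pacing". It gives no paced-beat percentage and does not mention post-dose tracings.

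QTcF change from baseline and QTcF outliers are primary endpoints (Protocol 3.0). Under Protocol 4.6, a QTcF above 500 msec or more than 60 msec over baseline is guidance for a possible DLAE, "based on an average QTcF value of triplicate ECGs". No exception is made for paced tracings.

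SAP VII.G recognises the problem. It expects that many HFrEF patients with sequential pacemakers or resynchronisation devices "may be unevaluable with respect to QT/QTc analysis due to the inherently prolonged and fixed QRS configuration". It therefore presents the ECG analysis twice, once for all subjects and once for those without a pacemaker or CRT. Protocol 9.4.3 provides for an analysis without paced ECGs where that is relevant.

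**The concern.** Pacing alters QRS and QT; a defibrillator that is not pacing does not. Criterion 5 attaches its limits to the defibrillator, so two subjects with the same pacing burden are treated differently according to the type of device.

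The difficult case for a change-from-baseline measure is an unpaced baseline followed by a paced post-dose tracing, because the difference then contains a device effect. In a JK07 subject it can look like a drug effect. In a placebo subject it can hide one. The groups are small: an unexpanded cohort has one sentinel and three randomised JK07 subjects. The DRC reads randomised subjects blinded by default (Protocol 9.6), so a device artefact could enter a dose-escalation discussion as a possible QTcF signal.

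**Working it through.** **1. Criterion 5 applied as a rule.** The documents state no figure to reproduce; the check is one of logic.

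| Subject | Paced share of beats | Criterion 5 |
|---|---|---|
| ICD | 15% or less, unpaced Day 1 ECG | met, at investigator discretion |
| ICD | above 15% | not met |
| Pacemaker or CRT-P, no ICD | any value from 0% to 100% | met |

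At the same burden above 15%, the ICD carrier fails and the pacemaker carrier passes.

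**2. Search for another limit.**
- Inclusion 2 and exclusion 10 disregard recent admissions for routine pacemaker-lead work, so pacemaker carriers are foreseen.
- Exclusion 11 rests on the investigator's opinion of the screening ECG and does not name pacing.
- Exclusion 12 sets QTcF ceilings (450 ms for males, 470 ms for females) up to randomisation. An unpaced tracing can pass them.
- Section 8.2.5 controls the screening and Day 1 baseline tracings only.

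None of these limits the paced share. A continuously paced subject should be stopped by 8.2.5; an intermittently paced one need not be.

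**3. Where the mixture goes.**
- *Summary tables:* covered in part by the no-pacemaker presentation and by Protocol 9.4.3. The SAP version removes whole subjects and finds them by searching the ECG evaluation text for device words.
- *Possible-DLAE comparison (Protocol 4.6):* no pacing rule.
- *C-QT model (SAP IX.B):* no pacing rule. Baseline QTc enters as a covariate, and paced post-dose values stay in the response.

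**4. Scale, for illustration only.** Protocol Table 2 has eight in-hospital post-dose ECG times: end of infusion, 0.5, 1, 2, 4, 8, 24 and 48 hours. If each time is paced with probability p, the expected number of paced times is 8p.
- p = 0.15 (the cap): 8 × 0.15 = 1.2.
- p = 0.60 (assumed): 8 × 0.60 = 4.8. Under independence, such a subject would be unpaced at both screening and baseline with probability 0.4 × 0.4 = 0.16, so 8.2.5 would remove most subjects like this.

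If pacing lengthens QTcF by d ms in one subject at one time, the mean of n subjects moves by d/n. The documents give no value for d. Taking 40 to 80 ms purely as an assumption:
- n = 4 (1 sentinel + 3 randomised): 40/4 = 10 ms to 80/4 = 20 ms.
- n = 7 (expanded cohort, 1 + 6): 40/7 = 5.7 ms to 80/7 = 11.4 ms.

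**The case against.** The strongest reply is that eligibility requires every criterion and protocol requirement to be met, not criterion 5 alone. Section 8.2.5 already asks for unpaced screening and baseline ECGs whatever the device, and Protocol 8.0 allows no waivers. The ECG summaries are already presented with and without device carriers, paced ECGs can be excluded under 9.4.3, and the study tests no formal hypothesis. This stands to a large extent. It narrows the gap to subjects without an ICD who are paced intermittently and happen to be unpaced at both screening and baseline.

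It does not close the gap. The analysis safeguards act after enrolment and on the summary tables. They do not reach the C-QT model or the tracings the DRC considers during escalation.

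Four stronger readings are tempting, and the documents do not support them:
- *That any paced subject without an ICD can enter.* Section 8.2.5 should stop continuous pacing.
- *That the SAP declares such subjects unevaluable.* It says only that they may be.
- *That a 10 to 20 ms shift in a cohort mean breaches the SAP's 10 ms threshold.* That threshold is compared with the upper bound of the two-sided 90% interval for model-derived, placebo-corrected QTc, not with a raw group mean.
- *That a paced rise above 60 msec is automatically a DLAE.* Protocol 4.6 also requires at least possible relatedness, and the DRC makes the final determination. Tracings are also read on site and by a central reader.

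**Conclusion.** The point holds in a limited form. The 15% limit depends on having an ICD, and no other provision limits pacing burden in a subject with a pacemaker or CRT-P alone. An intermittently paced subject of this kind can carry an unpaced baseline into paced post-dose tracings. That affects QTcF change from baseline, the 60 msec possible-DLAE comparison and the C-QT model; only the summary tables have a partial safeguard.

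The size cannot be calculated from the documents. They give no QTcF effect of pacing, no pacing burden and no count of pacemaker-only candidates. The 40 to 80 ms shift and the 60% burden are assumptions, and pacing at successive times need not be independent. The conclusion rests on the wording of the rules, not on those figures. This is a cheap improvement, not a flaw that undermines the study.

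**What to change.** 1. Reconcile criterion 5 with Protocol 8.2.5 and SAP VII.G by applying the two existing conditions to any implanted device that can pace (ICD, CRT-D, CRT-P, pacemaker). No new limit is needed, and every subject already wears the e-Patch that measures the paced share.
2. State in SAP IX.B that the exclusion of paced ECGs in Protocol 9.4.3 also applies to the C-QT model. The SAP may be modified until database lock, so this does not depend on a protocol amendment.
3. Reconcile the QTcF item in the Protocol 4.6 DLAE guidance with that exclusion by flagging paced tracings to the DRC. The judgement stays with the DRC.

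Step 1 alone is not enough: even at the 15% cap about 1.2 of the eight in-hospital post-dose times would be expected to be paced, which is why steps 2 and 3 are included.

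The cost is a line in the next protocol amendment, a sentence in the SAP and a flag in the DRC data displays. Some pacemaker-only candidates would no longer qualify; the documents do not say how many.

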### 9.2 Sample Size Determination

The study will enroll up to a maximum of 63 subjects who will be randomized into dose escalation cohorts. The sample size is not based on statistical considerations but is typical for studies of this nature and is considered adequate to characterize the distribution of the planned endpoints. Any statistical testing will be considered exploratory and descriptive.

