## **B. Study Population**

Individuals eligible to participate in this study must meet the criteria listed in Sections 5.1 and 5.2 of the Protocol.

All relevant medical and non-medical conditions will be taken into consideration when the decision is made upon whether this Protocol is suitable for a subject. Eligibility criteria may not be waived.

Screen failures are defined as subjects who consent to participate in the clinical study but are not subsequently assigned to study treatment. A minimal set of screen failure information is required to ensure transparent reporting of screen failure subjects to meet the Consolidated Standards of Reporting Trials publishing requirements and to respond to queries from regulatory authorities. Minimal information includes demography, screen failure details, eligibility criteria, and any SAE.

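### Inclusion criterion 7 states its platelet and ANC limits in units that cannot both be right: as printed, no subject can meet the platelet limit and the ANC limit screens out almost no one

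*Protocol*

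**What the plan says.** Protocol Section 5.1, criterion 7, requires a screening hemoglobin of at least 9.0 g/dL and then gives two cell-count limits, both per mL: "\geq 100 \times 10^9 / \text{mL}$ , ANC" for platelets (at least 100 x 10^9/mL), followed by an ANC of at least 1500/mL.

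The list is binding: "Subjects are eligible to be included in the study only if all of the following criteria apply". Section 5.0 adds that advance approval of departures from the entry criteria, "also known as protocol waivers or exemptions, is not permitted". The SAP (IV.B, Study Population) repeats the rule: "Eligibility criteria may not be waived".

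Section 4.6 uses a different unit for ANC. Its guidance on possible dose-limiting adverse events (DLAEs) begins with "Any febrile neutropenia [absolute neutrophil count (ANC" and puts the ANC component below 1000/mm3, together with a temperature above 38.3 °C for more than 1 hour.

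No other current section restates the criterion 7 limits in another unit. The Amendment 3 change list for Section 5.1 covers criteria 2, 4, 5 and 6, not 7.

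**The concern.** These are numeric entry thresholds in a first-in-human study whose primary objective is safety. As printed, one cannot be met and the other does almost no screening. Screening hematology is run by local laboratories (Appendix 3, Table 14) at about 8 centers, and each center has to decide for itself what the criterion means. If centers decide differently, subjects are admitted under different limits with no record of which was used.

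The SAP depends on the criterion for accounting. Section VI.B tabulates screen failures by failed criterion, and VI.C summarizes minor and major protocol deviations separately. Protocol Section 7.1 says that a subject found before dosing not to meet the enrollment criteria should be discontinued. None of this can be applied consistently to platelets while the written limit is unattainable.

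**Working it through.** The check is unit conversion, with 1 L = 1000 mL and 1 mL = 1000 mm3 = 1000 µL. The plan derives no figure of its own for this criterion, so there is none to reproduce.

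**Inputs from the documents**
- Platelet limit: 100 x 10^9/mL (Protocol 5.1, criterion 7)
- ANC limit: 1500/mL (same criterion)
- ANC component of the febrile neutropenia item: 1000/mm3 (Protocol 4.6)

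**Assumed inputs, because the documents give none**
- Usual adult platelet count: 150 to 400 x 10^9/L
- Extreme platelet count: 2000 x 10^9/L
- Mean platelet volume: 5 to 12 fL

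**Platelets**
- 100 x 10^9/mL x 1000 mL/L = 10^14/L = 100,000 x 10^9/L.
- Against the usual range: 100,000/400 = 250 and 100,000/150 = 667, so the limit is about 250 to 670 times a usual count.
- Against the extreme count: 100,000/2000 = 50 times.
- Volume check: 10^11 platelets per mL x 5 fL (5 x 10^-12 mL) = 0.5 mL of platelets per mL of blood; at 12 fL it is 1.2 mL per mL. The low end would make half of the blood platelets, and the high end exceeds the whole volume.

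**ANC**
- 1500/mL ÷ 1000 = 1.5/mm3.
- The Section 4.6 component in the same unit: 1000/mm3 x 1000 = 1,000,000/mL.
- Ratio: 1,000,000/1500 = 667.
- Subjects with an ANC of 2, 10, 100, 500 or 999/mm3 all satisfy the limit as printed. One with 1/mm3 does not.

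**Can one shared unit repair both limits?**

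| Unit applied to both | Platelet limit | ANC limit |
|---|---|---|
| per mL (as printed) | 100,000 x 10^9/L | 1.5/mm3 |
| per L | 100 x 10^9/L | 0.0015/mm3 |
| per µL (= mm3) | 100,000,000 x 10^9/L | 1500/mm3 |

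Every row leaves at least one limit unusable, so the two analytes need different denominators.

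**The case against.** **Extraction error.** The text was read from PDF, and a lost micro sign could turn µL into mL. For ANC this stands: the printed unit may not be the sponsor's, and the source should be checked. For platelets it makes matters worse, since per µL raises that limit another 1000-fold.

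**Excludes nobody.** A reader might say the ANC limit excludes no one at all. That is slightly too strong, because an ANC below 1.5/mm3 still fails.

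**Entry below a toxicity limit.** A reader might infer that subjects can enter already at a level the protocol counts as a DLAE. Section 4.6 does not support this. The item needs fever as well as a low ANC, as a new finding in an event at least possibly related to the product. A stable low count before dosing does not meet it. The 667-fold ratio shows the unit mismatch and does not measure risk.

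**No protection.** Exclusion 24 bars clinically significant hematological disease as judged by the investigator. Screening hematology includes neutrophils, and Section 8.2.7 requires laboratory reports to be reviewed. This is a real second barrier, but it is discretionary and carries no number.

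**Waivers.** The ban covers enrolling subjects who fail a criterion. It does not stop the sponsor from correcting a unit, and Appendix 2 allows administrative changes that leave benefit/risk unaffected without a formal amendment.

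**Analyses.** The Safety and DLAE populations do not depend on criterion 7. PK and PD exclusions apply only to deviations thought to affect those results (SAP V.K), and a subject already dosed stays in the study (Protocol 7.1). The documents do not show that any analysis is biased.

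**Conclusion.** The point holds as a unit error in a binding entry criterion. The platelet unit is wrong on its face: the limit is 1000 times the same number read per L, and it remains 50 times an assumed extreme count. That conclusion rests on assumed physiological ranges, but it holds across every value tried. The ANC limit as printed, 1.5/mm3, is close to no limit and does not match the unit in Section 4.6. This half is less certain until the source document is checked.

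A reader might infer that nobody can be enrolled, or that every enrolled subject is a protocol violator. That is only the formal consequence of the literal text. Sites probably apply the units their laboratories report. The likely harm is therefore inconsistent or undocumented eligibility decisions and misclassified deviations; the documents do not show that this has happened.

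**What to change.** 1. Check the units of criterion 7 in the source protocol, particularly for ANC.
2. Have the sponsor confirm the intended platelet and ANC limits, and restate each with its own unit by amendment or clarification letter, in units that local laboratories report.
3. Reconcile the ANC unit with the per-mm3 unit in Section 4.6.
4. Re-check existing screening hematology against the corrected criterion, so that screen failures and deviations are classified correctly under SAP VI.B and VI.C.

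The cost is one line of protocol text and a review of results already held. No new test is needed. The choice of clinical limit stays with the sponsor.
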